5.1.2 Subject Inclusion Criteria

In order to be eligible for participation in this trial, the subject must:

1. Be willing and able to provide written informed consent/assent for the trial.
2. Be ≥ 18 years of age on day of signing informed consent.
3. Must have measurable disease defined by at least one of the following criteria:
 - a. Lesions greater than 1.5 cm that can be accurately measured in two dimensions by CT (preferred), or MRI.
4. Must have indication for treatment (Adapted from NCCN 2015 Guidelines)
Any of the following constitute an indication for treatment:
 - a. Significant symptoms due to any iBCL: Which may include pain/discomfort, limitation of function, fatigue/malaise/constitutional symptoms, B-symptoms (fever, weight loss, night sweats), pruritus;
 - b. Threatened end-organ function due to any iBCL;
 - c. Progressive cytopenia secondary to any iBCL;
 - d. Steady progression of FL and MZL
5. Have a performance status of 0 or 1 on the ECOG Performance Scale.
6. Demonstrate adequate organ function as defined in Table 1.

Table 1 Adequate Organ Function Laboratory Values

System	Laboratory Value
Hematological	
Absolute neutrophil count (ANC)	$\geq 500/\mu\text{L}$ ^{a, b}
Platelets	$\geq 25\,000/\mu\text{L}$ ^{a, b}
Hemoglobin	$\geq 8\text{ g/dL}$ ^{a, b}
Renal	

Creatinine Measured or calculated ^a creatinine clearance (GFR can also be used in place of creatinine or CrCl)	OR $\leq 1.5 \times$ ULN $\geq 30 \text{ mL/min}$ for participant with creatinine levels $> 1.5 \times$ institutional ULN
Hepatic	
Total bilirubin	$\leq 1.5 \times$ ULN OR direct bilirubin \leq ULN for participants with total bilirubin levels $> 1.5 \times$ ULN
AST (SGOT) and ALT (SGPT)	$\leq 2.5 \times$ ULN ($\leq 5 \times$ ULN for participants with liver metastases)
Coagulation	
International normalized ratio (INR) OR prothrombin time (PT) Activated partial thromboplastin time (aPTT)	$\leq 1.5 \times$ ULN unless participant is receiving anticoagulant therapy as long as PT or PTT is within therapeutic range of intended use of anticoagulants
ALT (SGPT)=alanine aminotransferase (serum glutamic pyruvic transaminase); AST (SGOT)=aspartate aminotransferase (serum glutamic oxaloacetic transaminase); GFR=glomerular filtration rate; ULN=upper limit of normal.	
^a Growth factor and/or transfusion support is permissible to stabilize participant prior to study treatment if needed.	
^b No lower limit if cytopenia is related to bone marrow involvement.	

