5.2.1.2 Dose Modification

Adverse events (both non-serious and serious) associated with pembrolizumab exposure may represent an immunologic etiology. These adverse events may occur shortly after the first dose or several months after the last dose of treatment. Pembrolizumab must be withheld for drug-related toxicities and severe or life-threatening AEs as per Table 3 below. See Section 5.6.1 and Events of Clinical Interest Guidance Document for supportive care guidelines, including use of corticosteroids.

Table 3
Dose Modification Guidelines for Drug-Related Adverse Events

General instructions:				
Immune-related AEs	Toxicity grade or conditions (CTCAEv4.0)	Action taken to pembrolizumab	irAE management with corticosteroid and/or other therapies	Monitor and follow-up
Pneumonitis	Grade 2	Withhold	
 Administer corticosteroids (initial dose of 1-2 mg/kg prednisone or equivalent) followed by taper Add prophylactic antibiotics for opportunistic infections 	
 Monitor participants for signs and symptoms of pneumonitis Evaluate participants with suspected pneumonitis with radiographic imaging and initiate corticosteroid treatment
	Grade 3 or 4, or recurrent Grade 2	Permanently discontinue		
Diarrhea / Colitis	Grade 2 or 3	Withhold	
 Administer corticosteroids (initial dose of 1-2 mg/kg prednisone or equivalent) followed by taper 	
 Monitor participants for signs and symptoms of enterocolitis (ie, diarrhea, abdominal pain, blood or mucus in stool with or without fever) and of bowel perforation (ie, peritoneal signs and ileus).

	Grade 4 or recurrent Grade 3	Permanently discontinue		
 Participants with \geq Grade 2 diarrhea suspecting colitis should consider GI consultation and performing endoscopy to rule out colitis. Participants with diarrhea/colitis should be advised to drink liberal quantities of clear fluids. If sufficient oral fluid intake is not feasible, fluid and electrolytes should be substituted via IV infusion.
AST / ALT elevation or Increased bilirubin	Grade 2 ^a	Withhold	
 Administer corticosteroids (initial dose of 0.5- 1 mg/kg prednisone or equivalent) followed by taper 	
 Monitor with liver function tests (consider weekly or more frequently until liver enzyme value returned to baseline or is stable

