Exfoliative Dermatologic Conditions	Suspected SJS, TEN, or DRESS	Withhold	
 Based on severity of AE administer corticosteroids 	
 Ensure adequate evaluation to confirm etiology or exclude other causes
	Confirmed SJS, TEN, or DRESS	Permanently discontinue		
All other irAEs	Persistent Grade 2	Withhold	
 Based on type and severity of AE administer corticosteroids 	
 Ensure adequate evaluation to confirm etiology and/or exclude other causes
	Grade 3	Withhold or discontinue based on the type of event ^a .		
	Grade 4 or recurrent Grade 3	Permanently discontinue		

AE(s)=adverse event(s); ALT= alanine aminotransferase; AST=aspartate aminotransferase; CTCAE=Common Terminology Criteria for Adverse Events; DRESS=Drug Rash with Eosinophilia and Systemic Symptom; GI=gastrointestinal; IO=immuno-oncology; ir=immune related; IV=intravenous; SJS=Stevens-Johnson Syndrome; T1DM=type 1 diabetes mellitus; TEN=Toxic Epidermal Necrolysis; ULN=upper limit of normal.

Note: Non-irAE will be managed as appropriate, following clinical practice recommendations.

^a AST/ALT: >3.0 to 5.0 x ULN if baseline normal; >3.0 to 5.0 x baseline, if baseline abnormal; bilirubin: >1.5 to 3.0 x ULN if baseline normal; >1.5 to 3.0 x baseline if baseline abnormal

^b AST/ALT: >5.0 to 20.0 x ULN, if baseline normal; >5.0 to 20.0 x baseline, if baseline abnormal; bilirubin: >3.0 to 10.0 x ULN if baseline normal; >3.0 to 10.0 x baseline if baseline abnormal

^c AST/ALT: >20.0 x ULN, if baseline normal; >20.0 x baseline, if baseline abnormal; bilirubin: >10.0 x ULN if baseline normal; >10.0 x baseline if baseline abnormal

^d The decision to withhold or permanently discontinue pembrolizumab is at the discretion of the investigator or treating physician. If control achieved or \leq Grade 2, pembrolizumab may be resumed.

^e Events that require discontinuation include, but are not limited to: encephalitis and other clinically important irAEs (e.g., vasculitis and sclerosing cholangitis).

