If the study is stopped due to lack of efficacy in a histologic subgroup, the study may only be reopened to accrual for patients with that histology with modifications (e.g. addition of a

second agent, change in dosing, etc) that have been reviewed and approved where appropriate by the sponsor, scientific review, and relevant regulatory bodies.

Suspension rules for toxicity:

Prior studies treating patients that have not received prior chemotherapy suggest that the rates of grade ≥ 3 immune-related AEs occur in approximately 10% of patients (Reck et al, NEJM 2016). Infusion reactions of \geq grade 3 are less common and less consistently reported in publications. For this reason, we will initiate a suspension rule for infusion- or immune-related AEs of \geq grade 3 of up to 12%. This will be deemed to occur if the lower level of a one-sided 80% confidence interval for immune-related or infusional AEs of \geq grade 3 exceeds 12%.

Operationally, the study will be suspended and referred to the DSMC for consideration of results and appropriate modification or termination of the study if

- 3 out of the first 11 or fewer, 5 out of the first 22 or fewer, 6 out of the first 33 or fewer have \geq grade 3 immune related or infusional AEs

If the true probability of \geq grade 3 AEs is 5%, the probability of suspending the trial due to excess AEs after 11, 22, and 33 patients is approximately <0.02, 0.02, and 0.02, respectively. If the true probability of \geq grade 3 AEs is 30%, the probability of suspension due to excess AE is approximately 0.80, 0.94, and 0.99, respectively. (Probabilities of suspension estimated from 5,000 simulations).

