Each of the events above is described within this guidance document, along with site requirements for reporting these events to the Sponsor. The information collected should be entered into the narrative field(s) of the Adverse Event module in the database (please note, if narrative entry into the database is not available, please use the narrative text box on the 1727/AER Form). If additional Medical History or Concomitant Medications are reported, the Medical History and Concomitant Medication modules in the database must be updated.

In addition, the guidelines include recommendations on the management of these ECIs. These guidelines are intended to be applied when the physician determines the events to be related to pembrolizumab. Note: if after the evaluation the event is determined not to be related, the physician is instructed to follow the ECI reporting guidance but does not need to follow the treatment guidance (below). Therefore, these recommendations should be seen as guidelines and the treating physician should exercise individual clinical judgment based on the patient. For any question of dose modification or other treatment options, the specific language in the

protocol should be followed. Any questions pertaining to the collection of this information or management of ECIs should be directed to your local Sponsor contact.

Dose Modification/Discontinuation

The treatment guidance provides specific direction when to hold and/or discontinue pembrolizumab for each immune related adverse event. Of note, when the guidance states to “discontinue” pembrolizumab this is the permanent discontinuation of treatment with pembrolizumab. “Hold” means to stop treating with pembrolizumab but resumption of treatment may be considered assuming the patient meets the criteria for resumption of treatment.

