3.5 Hepatic

The following AE terms, if considered \geq Grade 2 or greater (or any grade with dose modification or use of systemic steroids to treat the AE), are considered ECIs and should be reported to the Sponsor within 2 business days of the event:

- Autoimmune hepatitis
- Hepatitis
- Transaminase elevations

All attempts should be made to rule out other causes such as metastatic disease, infection or other hepatic diseases. However, the AE should be reported regardless of etiology.

Drug Induced Liver Injury (DILI)

In addition, the event must be reported as a Drug Induced Liver Injury (DILI) ECI, if the patient meets the laboratory criteria for potential DILI defined as:

- An elevated alanine transaminase (ALT) or aspartate transaminase (AST) lab value that is greater than or equal to three times (3X) the upper limit of normal (ULN) and
- An elevated total bilirubin lab value that is greater than or equal to two times (2X) ULN and
- At the same time, an alkaline phosphatase (ALP) lab value that is less than 2X ULN,
- As a result of within-protocol-specific testing or unscheduled testing.

Note that any hepatic immune ECI meeting DILI criteria should only be reported once as a DILI event.

Course of Action

Grade 2 events:

- Report as ECI
- Hold pembrolizumab when AST or ALT >3.0 to 5.0 times ULN and/or total bilirubin >1.5 to 3.0 times ULN. In the case of Gilbert's syndrome where baseline bilirubin > 1.5 ULN, hold pembrolizumab when bilirubin > 1.5 to 3.0 times baseline level
- Monitor liver function tests more frequently until returned to baseline values (consider weekly).
 - Treat with 0.5-1 mg/kg/day methylprednisolone or oral equivalent and when LFT returns to grade 1 or baseline, taper steroids over at least 1 month, consider prophylactic antibiotics for opportunistic infections, and resume pembrolizumab per protocol
- Permanently discontinue for inability to reduce corticosteroid dose to 10 mg or less of prednisone or equivalent per day within 12 weeks.
- Permanently discontinue pembrolizumab for patients with liver metastasis who begin treatment with Grade 2 elevation of AST or ALT, and AST or ALT increases $\geq 50\%$ relative to baseline and lasts ≥ 1 week.

Grade 3 events:

- Report as ECI
- Discontinue pembrolizumab when AST or ALT >5.0 times ULN and/or total bilirubin >3.0 times ULN.
- Consider appropriate consultation and liver biopsy to establish etiology of hepatic injury, if necessary

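### With a raised baseline AST/ALT, Table 3 and the ECI guidance grade the same liver value differently, and Section 8.2 does not say which grade counts

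*Combined protocol and SAP*

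**What the plan says.** **Table 3 (Section 5.2.1.2).** The toxicity column is labelled CTCAE v4.0. Its hepatic footnotes switch to the patient's own baseline when that baseline is abnormal. Grade 2 is "AST/ALT: >3.0 to 5.0 x ULN if baseline normal; >3.0 to 5.0 x baseline, if baseline abnormal" and Grade 3 is "AST/ALT: >5.0 to 20.0 x ULN, if baseline normal; >5.0 to 20.0 x baseline, if baseline abnormal".

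**ECI guidance, Section 3.5 (Appendix 11.5).** Under its Grade 2 heading: "Hold pembrolizumab when AST or ALT >3.0 to 5.0 times ULN". Under its Grade 3 heading: "Discontinue pembrolizumab when AST or ALT >5.0 times ULN and/or total bilirubin >3.0 times ULN". These AST/ALT bands do not move with baseline. Two other provisions do refer to baseline. One is a bilirubin adjustment for Gilbert's syndrome at Grade 2. The other is a separate discontinuation rule for liver-metastasis patients who start treatment at Grade 2 and then rise by 50% or more over baseline for at least a week.

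**Entry criteria (Section 5.1.2, Table 1).** AST/ALT may be up to 2.5 x ULN, or up to 5 x "ULN for participants with liver metastases".

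**Suspension rule (Section 8.2).** The count is of patients with at least "grade 3 immune related or infusional AEs", with boundaries 3/11, 5/22 and 6/33. No hepatic scale is named.

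**Grading standard.** Sections 7.1.2.1, 7.2.4 and 11.2 say that adverse events are graded by CTCAE v4.0. The hepatic cut-offs are not printed.

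**The concern.** The entry criteria admit patients for whom the two hepatic scales disagree. The ECI guidance speaks of patients who start treatment at Grade 2, which is possible on a ULN scale but not on a multiple-of-baseline scale. So the two texts do grade differently.

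The recorded grade is used in three places:

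- **Capture.** Sections 7.2 and 7.2.5 single out Grade 3 or higher events and ECIs. The ECI table lists hepatic events from Grade 2 upward, or at any grade that leads to dose modification or systemic steroids, and ECIs are due within 2 business days.
- **Severity tables.** Section 8.3.2.4 summarises events by severity.
- **Suspension count.** Section 8.2 counts immune-related events from Grade 3 upward.

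Identical laboratory data could therefore give two different counts for a safety rule.

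**Working it through.** **Step 1. Map the grades.** Let b be the baseline and v the on-study value, both in multiples of ULN, with b above 1.

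- Table 3: Grade 2 if 3b < v ≤ 5b; Grade 3 if 5b < v ≤ 20b.
- ECI 3.5: Grade 2 if 3 < v ≤ 5; Grade 3 if v > 5 (no numerical cut-off is given for Grade 4).
- Grade 3 in the guidance but lower in Table 3: 5 < v ≤ 5b.
- Grade 3 in the guidance but below Grade 2 in Table 3: 5 < v ≤ 3b, which needs b > 5/3 = 1.67.

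| Baseline b | Table 3 Grade 2 | Table 3 Grade 3 starts | Discordant at Grade 3 |
|---|---|---|---|
| 1.2 | >3.6 to 6 | >6 | >5 to 6 |
| 1.5 | >4.5 to 7.5 | >7.5 | >5 to 7.5 |
| 2.0 | >6 to 10 | >10 | >5 to 10 |
| 2.5 | >7.5 to 12.5 | >12.5 | >5 to 12.5 |
| 5.0 (liver metastases) | >15 to 25 | >25 | >5 to 25 |

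With a normal baseline the band is empty and the scales agree.

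Two examples:

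- Baseline 2, value 9: 9/2 = 4.5 x baseline. Table 3 gives Grade 2; ECI 3.5 gives Grade 3.
- Baseline 2.5, value 6.5: 6.5/2.5 = 2.6 x baseline. This is below Grade 2 in Table 3 and Grade 3 in ECI 3.5.

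**Step 2. Reproduce the suspension boundary.** Section 8.2 triggers when the one-sided 80% lower limit exceeds 12%. The exact limit for x events in n patients is the 20th percentile of Beta(x, n − x + 1).

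| At boundary | Lower limit | One event fewer | Lower limit |
|---|---|---|---|
| 3/11 | 0.143 | 2/11 | 0.076 |
| 5/22 | 0.144 | 4/22 | 0.106 |
| 6/33 | 0.1204 | 5/33 | 0.095 |

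The stated boundary reproduces. At each look, one event fewer falls below 12%. The suspension probabilities for a 5% true rate also reproduce: 0.015, 0.017 and 0.020 exact, against <0.02, 0.02 and 0.02 stated. Those for a 30% rate do not: 0.687, 0.869 and 0.966 exact, against 0.80, 0.94 and 0.99. That is a separate matter, and nothing here depends on it.

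**Step 3. Illustrate the size, under assumptions.** The documents give no share of patients with an abnormal baseline. Assume:

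- a 10% rate of counted events on the Table 3 scale (Section 8.2 expects about 10% for immune-related events);
- a share f of 5% to 20% with abnormal baseline;
- a chance h of 10% to 30% that such a patient has an immune-related value in the discordant band and no other counted event.

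The rate on the ULN scale is 0.10 + f × h:

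- low end: 0.10 + 0.05 × 0.10 = 0.105;
- high end: 0.10 + 0.20 × 0.30 = 0.16.

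The cumulative probability of suspension by 33 patients is 0.163 at a rate of 10%, 0.186 at 10.5% and 0.504 at 16%. The expected number of reclassified patients is 33 × f × h, or 0.17 to 1.98.

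**The case against.** **Dosing already has a precedence rule.** The ECI overview sends questions of dose modification to the protocol's own language and calls its recommendations guidelines. Section 5.2.1.2 makes Table 3 govern withholding. This stands. A reader might infer that a patient would be held, discontinued or left on treatment according to which page the site opens, and might cite the overview's sentence "The treatment guidance provides specific direction when to hold and/or discontinue pembrolizumab for each immune related adverse event". That sentence does not cancel the precedence rule, so the documents do not support the inference. The rule is, however, silent on the grade to be recorded or counted.

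**CTCAE v4.0 is the named standard, and the ECI figures are action triggers under grade headings.** Both statements are true. They do not settle the grade, because Table 3 gives its baseline multiples the CTCAE v4.0 label while the guidance grades on ULN, and no cut-offs are printed to choose between them.

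**The guidance does not ignore baseline.** A reader might infer that it makes no allowance for a raised baseline. The Gilbert's syndrome and liver-metastasis provisions show otherwise. The liver-metastasis rule has no counterpart in Table 3 and also needs reconciling.

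**Pre-dose values.** A reader might infer that a patient enrolled at 4 x ULN is already in the guidance's hold band before the first dose. The guidance applies to events judged related to pembrolizumab, and a pre-dose value cannot be.

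**Few patients, and no automatic stop.** Only abnormal baselines matter, and known active hepatitis B and C are excluded. An event counts only if it is also immune-related. Crossing the boundary suspends the trial for DSMC review and does not end it. That one event can tip a count is true of any boundary. All of this limits the size but does not remove the ambiguity.

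**Events need not be lost.** Section 7.1.5.3 asks for all adverse events before the end-of-treatment visit, and liver tests are scheduled with the treatment cycles. The tables could be regraded later. A suspension rule applied during accrual cannot wait for that.

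**Conclusion.** Wrong as written: the documents contradict themselves on hepatic grading when baseline AST/ALT is abnormal. The discordant band at Grade 3 runs from above 5 to 5b x ULN. It reaches 12.5 x ULN at the general entry limit and 25 x ULN at the liver-metastasis limit. The main unresolved effect is on the recorded grade: whether the event is captured as a Grade 3 event or an ECI, how it is tabulated, and whether it counts toward suspension if immune-related.

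The grade map and the boundary follow from the printed figures. The shift in suspension probability from 0.163 to between 0.186 and 0.504 rests wholly on the assumed shares and is not an estimate for this trial. The affected number may be small. This is a low-cost correction worth making to protect a safety rule, not a defect that undermines the design.

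**What to change.** Reconcile Table 3 footnotes a to c with ECI guidance 3.5, including its liver-metastasis rule, so that both places state the same hepatic grading reference and the same treatment of an abnormal baseline. Add a sentence to Section 8.2 saying that this single reference is used for adverse event and ECI recording, for the severity tables and for the suspension count. The choice of thresholds belongs to the sponsor's clinical team.

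The cost is protocol and appendix wording. No extra tests are needed, because baseline and on-study liver tests are already scheduled.

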	Grade 3 ^b or 4 ^c	Permanently discontinue	
 Administer corticosteroids (initial dose of 1-2 mg/kg prednisone or equivalent) followed by taper 	
Type 1 diabetes mellitus (T1DM) or Hyperglycemia	Newly onset T1DM or Grade 3 or 4 hyperglycemia associated with evidence of β -cell failure	Withhold ^d	
 Initiate insulin replacement therapy for participants with T1DM Administer anti-hyperglycemic in participants with hyperglycemia 	
 Monitor participants for hyperglycemia or other signs and symptoms of diabetes.
Hypophysitis	Grade 2	Withhold	
 Administer corticosteroids and initiate hormonal replacements as clinically indicated. 	
 Monitor for signs and symptoms of hypophysitis (including hypopituitarism and adrenal insufficiency)
	Grade 3 or 4	Withhold or permanently discontinue ^d		
Hyperthyroidism	Grade 2	Continue	
 Treat with nonselective beta-blockers (eg, propranolol) or thionamides as appropriate 	
 Monitor for signs and symptoms of thyroid disorders.
	Grade 3 or 4	Withhold or permanently discontinue ^d		
Hypothyroidism	Grade 2-4	Continue	
 Initiate thyroid replacement hormones (eg, levothyroxine or liothyroinone) per standard of care 	
 Monitor for signs and symptoms of thyroid disorders.

Nephritis grading according to increased creatinine or acute kidney injury	Grade 2	Withhold	
 Administer corticosteroids (prednisone 1 to 2 mg/kg or equivalent) followed by taper. 	
 Monitor changes of renal function
	Grade 3 or 4	Permanently discontinue		
Neurological Toxicities	Grade 3 or 4	Permanently discontinue	
 Based on severity of AE administer corticosteroids 	
 Ensure adequate evaluation to confirm etiology and/or exclude other causes
Myocarditis	Grade 1	Withhold	
 Based on severity of AE administer corticosteroids 	
 Ensure adequate evaluation to confirm etiology and/or exclude other causes
	Grade 2, 3 or 4	Permanently discontinue		

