- All subjects who experience diarrhea/colitis should be advised to drink liberal quantities of clear fluids. If sufficient oral fluid intake is not feasible, fluid and electrolytes should be substituted via IV infusion. For Grade 2 or higher diarrhea, consider GI consultation and endoscopy to confirm or rule out colitis.
- For **Grade 2 diarrhea/colitis** that persists greater than 3 days, administer oral corticosteroids.
- For **Grade 3 or 4 diarrhea/colitis** that persists > 1 week, treat with intravenous steroids followed by high dose oral steroids.
- When symptoms improve to Grade 1 or less, steroid taper should be started and continued over no less than 4 weeks.

- **Type 1 diabetes mellitus (if new onset, including diabetic ketoacidosis [DKA]) or ≥ Grade 3 Hyperglycemia, if associated with ketosis (ketonuria) or metabolic acidosis (DKA)**

- For **T1DM or Grade 3-4 Hyperglycemia**
 - Insulin replacement therapy is recommended for Type I diabetes mellitus and for Grade 3-4 hyperglycemia associated with metabolic acidosis or ketonuria.
 - Evaluate patients with serum glucose and a metabolic panel, urine ketones, glycosylated hemoglobin, and C-peptide.

- **Hypophysitis:**

- For **Grade 2 events**, treat with corticosteroids. When symptoms improve to Grade 1 or less, steroid taper should be started and continued over no less than 4 weeks. Replacement of appropriate hormones may be required as the steroid dose is tapered.
- For **Grade 3-4 events**, treat with an initial dose of IV corticosteroids followed by oral corticosteroids. When symptoms improve to Grade 1 or less, steroid taper

should be started and continued over no less than 4 weeks. Replacement of appropriate hormones may be required as the steroid dose is tapered.

- **Hyperthyroidism or Hypothyroidism:**

Thyroid disorders can occur at any time during treatment. Monitor patients for changes in thyroid function (at the start of treatment, periodically during treatment, and as indicated based on clinical evaluation) and for clinical signs and symptoms of thyroid disorders.

- **Grade 2** hyperthyroidism events (and **Grade 2-4** hypothyroidism):

- In hyperthyroidism, non-selective beta-blockers (e.g. propranolol) are suggested as initial therapy.
 - In hypothyroidism, thyroid hormone replacement therapy, with levothyroxine or liothyroinine, is indicated per standard of care.

- **Grade 3-4** hyperthyroidism

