3.3 Endocrine

The following AE terms, if considered \geq Grade 3 or if \geq Grade 2 and require holding/discontinuation/ modification of pembrolizumab dosing, are considered ECIs and should be reported to the Sponsor within 2 business days of the event:

- Adrenal insufficiency
- Hyperthyroidism
- Hypophysitis
- Hypopituitarism
- Hypothyroidism
- Thyroid disorder
- Thyroiditis

All attempts should be made to rule out other causes such as brain metastases, sepsis and/or infection. However, the AE should be reported regardless of etiology.

Hypophysitis or other symptomatic endocrinopathy other than hypo- or

hyperthyroidism

Grade 2-4 events:

- Report as ECI if appropriate
- Hold pembrolizumab
- Rule out infection and sepsis with appropriate cultures and imaging.
- Monitor thyroid function or other hormonal level tests and serum chemistries more frequently until returned to baseline values.
- Pituitary gland imaging should be considered (MRIs with gadolinium and selective cuts of the pituitary can show enlargement or heterogeneity and confirm the diagnosis).
- Treat with prednisone 40 mg p.o. or equivalent per day. When symptoms improve to Grade 1 or less, steroid taper should be started and continued over no less than 4 weeks. Replacement of appropriate hormones may be required as the steroid dose is tapered.
- Permanently discontinue for inability to reduce corticosteroid dose to 10 mg or less of prednisone or equivalent per day within 12 weeks.
- Hypophysitis with clinically significant adrenal insufficiency and hypotension, dehydration, and electrolyte abnormalities (such as hyponatremia and hyperkalemia) constitutes adrenal crisis.
- Consultation with an endocrinologist may be considered.

Hyperthyroidism and Hypothyroidism

Thyroid disorders can occur at any time during treatment. Monitor patients for changes in thyroid function (at the start of treatment, periodically during treatment, and as indicated based on clinical evaluation) and for clinical signs and symptoms of thyroid disorders.

Grade 2 hyperthyroidism, Grade 2-4 hypothyroidism events:

- Report as ECI if appropriate (see Table 1)
- Monitor thyroid function or other hormonal level tests and serum chemistries more frequently until returned to baseline values.
- Thyroid hormone and/or steroid replacement therapy to manage adrenal insufficiency.
- Therapy with pembrolizumab can be continued while treatment for the thyroid disorder is instituted.

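### In Table 3, hypophysitis that has improved from Grade 3-4 to Grade 2 falls under both a line that requires a hold and a footnote that permits re-dosing

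*Combined protocol and SAP*

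**What the plan says.** Section 5.2.1.2 makes the table binding: "Pembrolizumab must be withheld for drug-related toxicities and severe or life-threatening AEs as per Table 3 below".

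Within Table 3, the first hypophysitis line reads "Hypophysitis Grade 2 Withhold". It carries no footnote and states no condition for restarting. The next line, for Grade 3 or 4 hypophysitis, reads "Withhold or permanently discontinue" and carries footnote d.

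Footnote d has two parts. The first gives the choice to the clinician: "The decision to withhold or permanently discontinue pembrolizumab is at the discretion of the investigator or treating physician". The second sets the restart condition: control achieved, or an event at or below "Grade 2, pembrolizumab may be resumed".

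Two other places deal with hypophysitis. Section 5.4.1 covers corticosteroids and hormone replacement. Section 3.3 of the ECI guidance (Appendix 11.5), under the heading that begins "Hypophysitis or other symptomatic endocrinopathy other than hypo- or", puts Grades 2 to 4 under a single hold instruction.

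**The concern.** A hold table has to give one answer for a patient's current state. Here, Grade 2 hypophysitis reached from above appears both as a grade at which drug is withheld and as a grade at which it may be given again.

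Two sites that each follow Table 3 could make opposite decisions about the same patient on the same day. A monitor could not say from the table which site had deviated. For a serious immune-related event this is a patient-safety matter first. It also affects the data: re-exposure, cycles received and recorded dose holds would depend on which line the site read.

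**Working it through.** There is no figure to recompute. The check sets the texts side by side.

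**Step 1: is the Grade 2 action mandatory?** Yes. Section 5.2.1.2 says drug must be withheld in accordance with Table 3, and the Grade 2 hypophysitis row says to withhold.

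**Step 2: does footnote d reach Grade 2 itself?** Yes. The threshold is less than or equal to Grade 2. It is joined to achieved control by the word *or*, so reaching Grade 2 is enough on its own terms.

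**Step 3: does the conflict extend to the other entries with footnote d?** Three events in Table 3 carry it.

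| Event carrying footnote d | Table 3 action for that event at Grade 2 | Conflict with resuming at or below Grade 2? |
|---|---|---|
| Hyperthyroidism, Grade 3 or 4 | "Hyperthyroidism Grade 2 Continue" | No |
| New-onset type 1 diabetes, or Grade 3 or 4 hyperglycemia with beta-cell failure | No Grade 2 row | No |
| Hypophysitis, Grade 3 or 4 | "Hypophysitis Grade 2 Withhold" | Yes |

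Only hypophysitis conflicts.

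**Step 4: does other text settle it?**

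- Section 5.4.1 says of hypophysitis: "When symptoms improve to Grade 1 or less, steroid taper should be started and continued over no less than 4 weeks". This concerns steroids and says nothing about when pembrolizumab restarts.
- Section 3.3 of the ECI guidance holds for Grades 2 to 4 but names no grade for restarting. The overview of that guidance defines a hold as a stop after which treatment may be considered again once resumption criteria are met, and it refers dose-modification questions to the protocol. That leads back to Table 3.
- Section 7.2.4 requires every change of grade within an episode to be recorded. The record of an improving patient would therefore show a current Grade 2 event, which the Grade 2 row covers as worded.

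Nothing in the available text says that footnote d overrides the Grade 2 row, or that the Grade 2 row applies only when an event first appears at that grade.

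**Step 5: how many patients?** The documents give no hypophysitis rate. Section 8.2 takes about 10% as the rate of Grade 3 or higher immune-related events of all kinds, so 0.10 × 33 = 3.3 patients would be expected across every type. Hypophysitis that reaches Grade 3-4 and then improves to Grade 2 is a subset of that.

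**Step 6: does it affect the statistical design?** No. Response rate is calculated over all treated patients (Section 8.3.1), so the patient stays in the denominator under either reading. The suspension rule in Section 8.2 counts Grade 3 or higher immune-related events whether or not dosing resumes. Sample size, power and type I error do not depend on the footnote.

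**The case against.** The best defence is that the two lines do different jobs. The Grade 2 row says what to do when an event is graded 2. Footnote d says when treatment may restart after a Grade 3-4 hold, and a specific restart rule can be an exception to a general trigger. The footnote is also permissive and leaves judgment with the physician. This reading is coherent and may be what was intended, but the available text does not state it, so a site cannot be expected to adopt it.

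A second point is that Table 3 opens with a line for general instructions under which no text appears in the copy reviewed, and several other Grade 2 hold rows also lack a restart condition. A general rule may have been lost in reading the file. The conclusion is limited accordingly to the text available.

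Four stronger readings are tempting, and the documents do not support them:

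- **That re-dosing at Grade 2 breaches the taper rule and the readings differ by more than a cycle.** A reader might set the 4-week minimum taper against the 3-week cycle. But Section 5.4.1 describes its measures as suggested, and no text ties restarting after hypophysitis to the start or end of a taper. The only steroid-linked dosing rule for hypophysitis in Section 3.3 of the ECI guidance is permanent discontinuation when the dose cannot be brought down to the stated level within 12 weeks.
- **That the ECI guidance independently contradicts footnote d.** Its hold instruction names no restart grade, and it defers to the protocol.
- **That a patient recovering from Grade 3-4 is treated more permissively than one who never exceeded Grade 2.** The Grade 2 row gives no restart condition, so the comparison depends on how that gap is filled.
- **That the protocol requires re-dosing at Grade 2.** Footnote d only allows it.

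**Conclusion.** The inconsistency is real and narrow. For hypophysitis that has improved from Grade 3-4 to Grade 2, one line of Table 3 requires a hold while its footnote d permits resumption, and the available text does not rank them. It is a contradiction in the wording of a dosing rule and does not reach the trial design.

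Few patients are likely to be affected, though the number cannot be calculated from the documents. It deserves correction because it concerns re-exposure after a serious immune-related event and is easy to put right. The conclusion assumes that no general instruction lost from the copy reviewed already resolves it. No view is taken on which line is clinically correct.

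**What to change.** The sponsor's medical team should reconcile the Grade 2 hypophysitis row with footnote d so that Table 3 gives one unambiguous action for hypophysitis that has improved from Grade 3-4 to Grade 2. It should then check that Section 5.4.1 and Section 3.3 of the ECI guidance agree with that action.

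Footnote d should stay unchanged for hyperthyroidism and for type 1 diabetes or hyperglycemia. It creates no conflict there, and the diabetes entry would lose its restart text if the footnote were removed. Which grade or condition should apply to hypophysitis is for the medical team to decide.

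The cost is a wording change to one row or one footnote and a consistency check of two other sections. It adds no procedures and does not change the sample size or the analysis.
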